5.1 Type of trial

This is a 26-week randomised, active-controlled, multicentre, multinational, two-arm parallel, open-label, TTT trial in subjects with T2DM. Subjects inadequately controlled on treatment with SGLT2i \pm OAD will be eligible for the trial. The trial will compare IDegLira to IGlar as an add-on to treatment with SGLT2i \pm OAD. Inadequately controlled T2DM is defined as an HbA_{1c} level of 7.0-11.0 % (53-97 mmol/mol) (both inclusive).

A total of 416 subjects will be randomized using IWRS in a 1:1 manner to either of the two trial arms, IDegLira (OD) or IGlar (OD).

[figure not shown]

Figure 5–1 Trial Design

The total trial duration will be approximately 32 weeks, consisting of a 2 week screening period, a 26-week treatment period, and two follow-up contacts (FU1 and FU2). FU1 is scheduled 7 days (+3 days) after last dose of trial product, and FU2 is scheduled 30 days (+3 days) after last dose of trial product. The purpose of FU1 and FU2 are to collect all treatment-emergent adverse events (AEs).

5.2 Rationale for trial design

Based on experience from previous insulin titration trials a duration of 26 weeks is sufficient to reach a stable HbA_{1c} level, i.e. minimum of 12 weeks in maintenance period and to obtain sufficient data for efficacy and safety evaluation.

The multinational approach is chosen to ensure that the results are applicable for subjects with different race and ethnicity, and to ensure that local regulatory requirements are fulfilled for a marketing approval.

Protocol Trial ID: NN9068-4229 UTN: U1111-1168-9343 EudraCT No.: 2015-001596-48

CONFIDENTIAL

Date: Version: Status: Page: 20 November 2015 2.0 Final 22 of 107

Novo Nordisk

The TTT approach and thereby the very high frequency of visits has been chosen in order to ensure optimal titration of IDegLira or IGlar based on pre-breakfast SMPG values and thereby to obtain improved HbA_{1c} results.

The primary endpoint, HbA_{1c}, is being assessed at a central laboratory, thus avoiding assessment bias.

The trial is open-label, as blinding the trial and including placebo would require a double dummy design with two s.c. injections, which is deemed to pose an unacceptable burden to the subjects and increase the trial design complexity, thereby increasing the risk of subjects withdrawing from the trial, discontinuing treatment prematurely or being non-compliant.

5.3 Treatment of subjects

Subjects with T2DM treated with SGLT2i and OAD(s) in accordance with the inclusion and exclusion criteria are eligible for the trial. When randomised the subjects will get one of the investigational medicinal products (IMPs) described below in combinations with previous SGTL2i \pm OAD. Pre-trial OAD treatments must include SGLT2i according to current local label, either as monotherapy, or in combination with metformin \pm DPP4i \pm pioglitazone. If a subject is treated with DPP4i these have to be discontinued at randomisation. Subjects on fixed dose combinations of SGLT2i and DPP4i should be shifted to the corresponding SGLT2i included in the original fixed dose combinations of SGLT2i and DPP4i. Pre-trial SGLT2i and metformin treatment should be continued at unchanged pre-trial doses throughout the trial, unless there is a safety concern. Pioglitazone is allowed in all subjects, except those treated with dapagliflozin, and pre-trial doses should be unchanged during the trial, unless there is a safety concern.

- IDegLira added to OAD therapy (SGLT2i ± OAD): IDegLira will be given s.c. once daily. The recommended starting dose of IDegLira is 10 dose steps (10 units insulin degludec/0.36 mg liraglutide). IDegLira will be titrated twice weekly according to a predefined titration algorithm, see appendix A, with a maximum dose of 50 dose steps (50 units insulin degludec/1.8 mg liraglutide) aiming to reach a pre-breakfast SMPG target between 4.0 5.0 mmol/L (72 90 mg/dL).
 - IGlar added to OAD therapy (SGLT2i ± OAD): IGlar will be given s.c. once daily. IGlar should be administered according to the approved label. The recommended starting dose of IGlar is 10 units and will be titrated twice weekly according to a predefined titration algorithm, see appendix A, with no maximum dose aiming to reach a pre-breakfast SMPG target between 4.0 5.0 mmol/L (72 90 mg/dL).

The IMPs used in this trial are described in section 9.

Protocol Trial ID: NN9068-4229 UTN: U1111-1168-9343

EudraCT No.: 2015-001596-48

CONFIDENTIAL

Date: Version: Status: Page:

20 November 2015 | Novo Nordisk 2.0 Final

23 of 107

5.4 Treatment after discontinuation of trial product

When discontinuing trial products, either prematurely or at V32 the subject should be switched to a suitable marketed product at the discretion of the investigator.

5.5 **Rationale for treatment**

IDegLira will be investigated in this trial to demonstrate efficacy and safety, when added to SGTL2i ± OAD in T2DM subjects, inadequately controlled on SGTL2i ± OAD. If a subject is treated with DPP4i these have to be discontinued at randomisation, as IDegLira cannot be combined with DPP4i.

IGlar has been chosen as comparator as it is currently a widely used basal insulin.

The TTT approach will be applied after randomisation in order to optimise glycaemic control throughout the trial.

All subjects in both arms will continue with SGTL2i ± OAD at pre-trial doses. In case of a safety concern the dose(s) may be reduced or temporarily interrupted at the discretion of the investigator. SGTL2i ± OAD treatment must follow the current locally approved label and any local recommendations present at the time of conducting the trial.

The duration of 26 weeks has been chosen to obtain a stabilised HbA_{1c} ensuring an adequate length of time of trial product at steady state.

Protocol Trial ID: NN9068-4229 UTN: U1111-1168-9343

EudraCT No.: 2015-001596-48

CONFIDENTIAL

Date: Version: Status: Page:

20 November 2015 | Novo Nordisk 2.0 Final

24 of 107

Trial population

6.1 Number of subjects

Number of subjects planned to be randomised and started on trial products: 416

Number of subjects expected to complete the trial (on trial product): 354

6.2 Inclusion criteria

For an eligible subject, all inclusion criteria must be answered "yes".

- 1. Informed consent obtained before any trial-related activities. Trial-related activities are any procedures that are carried out as part of the trial, including activities to determine suitability for the trial.
- 2. Male or female, age \geq 18 years at the time of signing informed consent.
- 3. Subjects diagnosed (clinically) with type 2 diabetes mellitus.
- 4. HbA_{1c} 7.0-11.0% (53-97 mmol/mol) (both inclusive) by central laboratory analysis.
- 5. BMI $\geq 20 \text{ kg/m}^2 \text{ and } \leq 40 \text{ kg/m}^2$.
- 6. Insulin naïve subjects; however short term insulin treatment for a maximum of 14 days prior to the day of screening is allowed, as well as prior insulin treatment for gestational diabetes.
- 7. Oral antidiabetic treatment:
 - SGLT2i: Subjects must have been on a stable daily dose of any SGLT2i (≥ half of the maximum approved dose according to current local label or maximum tolerated dose as documented in subject medical record, or minimum recommended maintenance* dose according to current local label) for at least 90 days prior to the day of screening.
 - b. Combination therapy: Stable daily dose of SGLT2i as outlined above in combination with stable daily dose(s) of metformin \pm DPP4i is allowed:
 - i. Metformin (≥ 1500 mg or maximum tolerated dose as documented in the subject medical record) for at least 90 days prior to the day of screening.
 - ii. DPP4i (≥ half of the maximum approved dose according to local label or maximum tolerated dose as documented in subject medical record) for at least 90 days prior to the day of screening.
 - iii. Stable daily doses, as outlined above, of fixed dose combination products combining either SGLT2i and metformin or SGLT2i and DPP4i, according to locally approved label for at least 90 days prior to the day of screening are also allowed.

Protocol	CONFIDENTIAL	Date:	20 November 2015	Novo Nordisk
Trial ID: NN9068-4229		Version:	2.0	
UTN: U1111-1168-9343		Status:	Final	
EudraCT No.: 2015-001596-48		Page:	25 of 107	

c. Pioglitazone: Stable daily dose (≥ half of the maximum approved dose according to local label or maximum tolerated dose as documented in subject medical record) for at least 90 days prior to the day of screening is allowed if a subject is treated with SGLT2i as outlined above, except in subjects treated with dapagliflozin.

* E.g. 100 mg Invokana® (canagliflozin) is recommended, but 300 mg is maximum approved dose.

6.3 Exclusion criteria

For an eligible subject, all exclusion criteria must be answered "no".

- 1. Known or suspected hypersensitivity to trial product(s) or related products.
- 2. Previous participation in this trial. Participation is defined as signed informed consent.
- 3. Receipt of any investigational medicinal product within 90 days prior to screening.
- 4. Female who is pregnant, breast-feeding or intends to become pregnant or is of child-bearing potential and not using adequate contraceptive methods (adequate contraceptive measures as required by local regulation or practice).
- 5. Use of any OADs (other than SGLT2i in monotherapy or in combination with metformin or DPP4i or pioglitazone as described in the inclusion criteria) within 90 days prior to the day of screening.
- 6. Use of GLP-1 receptor agonist (e.g., exenatide or liraglutide) within 90 days prior to the day of screening.
- 7. Acute decompensation of glycaemic control requiring immediate intensification of treatment to prevent severe metabolic dysregulation (e.g., diabetes ketoacidosis) in the previous 90 days prior to the day of the screening.
- 8. Family or personal history of multiple endocrine neoplasia type 2 or medullary thyroids carcinoma.
- 9. Screening calcitonin \geq 50 ng/L.
- 10. History of pancreatitis (acute or chronic).
- 11. Any of the following: myocardial infarction, stroke or hospitalisation for unstable angina and/or transient ischaemic attack within the past 180 days prior to the day of screening.
- 12. Subjects presently classified as being in NYHA Class III or IV.
- 13. Planned coronary, carotid or peripheral artery revascularisation at the day of screening.
- 14. Renal impairment eGFR < 60 mL/min/1.73 m² as per CKD-EPI.
- 15. Impaired liver function, defined as ALT \geq 2.5 times upper normal limit at screening.
- 16. Inadequately treated blood pressure as defined as Class 2 hypertension or higher (systolic ≥ 160 mmHg or diastolic > 100 mmHg) at screening.
- 17. Anticipated initiation or change in concomitant medications for more than 14 consecutive days or on a frequent basis known to affect weight or glucose metabolism (e.g., orlistat, thyroid hormones, corticosteroids).

- 18. Proliferative retinopathy or maculopathy requiring acute treatment. Verified by fundus photography or dilated fundoscopy performed within 90 days prior to randomisation.
- 19. History or presence of malignant neoplasms within the last 5 years (except basal and squamous cell skin cancer and in-situ carcinomas).
- 20. History of diabetic ketoacidosis.
- 21. Any disorder, except for conditions associated with diabetes, which in the investigator's opinion might jeopardise subject's safety or compliance with the protocol.

6.4 Premature discontinuation of trial product

All efforts should be made to keep the subject on trial product. Trial product must be discontinued if the subject meets rescue criteria or if the following applies:

 If the investigator suspects acute pancreatitis, all drugs suspected to relate to this condition must be discontinued until confirmatory tests have been conducted and appropriate treatment should be initiated

Trial product must be permanently discontinued if the following applies:

- Included in the trial in violation of the inclusion and/or exclusion criteria
- Pregnancy or intention to become pregnant
- Participation in other clinical trials throughout the trial
- In case the calcitonin value is ≥ 50 ng/L. Please see Appendix C
- Initiation or significant change in concomitant medications (in excess of 14 days) which in the investigator's opinion could affect weight or glucose metabolism
- Subjects that are diagnosed with acute pancreatitis (as a minimum 2 of 3: characteristic abdominal pain, amylase and/or lipase > 3x upper normal range or characteristic findings on ultrasound, computerised axial tomography /magnetic resonance imaging)

Permanent premature discontinuation of treatment with trial product will not lead to subject withdrawal from the trial. Trial product may be permanently discontinued at the discretion of the investigator due to a safety concern, unacceptable tolerability, or if a subject is judged to be non-compliant with trial procedures.

6.5 Rescue criteria

If the pre-breakfast SMPG values taken on three consecutive days or if any of the FPG samples analysed by the central laboratory exceeds the limit of:

- 15.0 mmol/L (270 mg/dL) from baseline to week 6
- 13.3 mmol/L (240 mg/dL) from week 7 to week 12
- 11.1 mmol/L (200 mg/dL) from week 13 to week 26

and if no treatable intercurrent cause for the hyperglycaemia has been identified, the subject should be called for a confirmatory FPG measurement as soon as possible. The FPG sample should be

Protocol Trial ID: NN9068-4229 UTN: U1111-1168-9343 EudraCT No.: 2015-001596-48

CONFIDENTIAL

Date: Version: Status: Page:

20 November 2015 | Novo Nordisk 2.0 Final 27 of 107

analysed by the central laboratory and if it exceeds the limits described above, the subject must discontinue treatment with trial product.

See procedures for premature discontinuation further described in section 8.1.7.

6.6 Withdrawal criteria

The subject may withdraw at will at any time.

A subject randomised in the trial in violation of the inclusion and/or exclusion criteria but not exposed to trial product must be withdrawn from the trial, and should not attend further visits.

A subject randomised in the trial in violation of the inclusion and/or exclusion criteria and exposed to trial product must discontinue treatment with trial product, but will not be withdrawn from the trial and will be followed as "premature discontinued of trial product" described in section 8.1.7.

Only subjects who decline any further contact with the site in relation to the trial, and hence do not agree to report information which is relevant for the assessments of trial end-points at the end of trial should be considered as withdrawn from the trial

Subjects who consider withdrawing informed consent should be encouraged to have procedures performed according to the EoT visit and the two follow-up contacts (see section 2).

Please see section 8.1.7 for procedures to be performed in case of subject withdrawal.

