8.1.7 Premature discontinuation of trial product

Subjects discontinuing trial product prematurely due to any of the rescue criteria (see section 6.5), criteria for premature discontinuation of trial product (see section 6.4) or at subjects own will, should be called in for an EoT visit corresponding to V32 as soon as possible after discontinuation of trial product, FU1 must be scheduled 7 days (+3 days) after discontinuation of trial product and FU2 must be scheduled 30 days (+3 days) after discontinuation of trial product.

Once the two follow-up contacts after discontinuation of trial product are completed the subject should be contacted by phone every 4 weeks. Information on antidiabetic medication and information on potential major cardiovascular events (MACE) and any SAEs occurring since last contact must be collected and recorded in the eCRF. Phone contacts must be documented in the medical record and in the eCRF. The subject should finally come in for a V32A at week 26 to report MACE, SAEs, total daily insulin dose, use of other antidiabetic medication, and have body weight measured and a blood sample taken to measure HbA_{1c}, see flow chart (section 2).

Final drug accountability must be done once the subject has discontinued the trial product and the premature discontinuation must be recorded in the IWRS through a treatment discontinuation session.

The reason for the premature discontinuation of trial product must be recorded in the eCRF.

Protocol Trial ID: NN9068-4229 UTN: U1111-1168-9343

EudraCT No.: 2015-001596-48

CONFIDENTIAL

Date: Version: Status: Page:

20 November 2015 | Novo Nordisk 2.0 Final 35 of 107

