8.1.8 Withdrawal of consent

If a subject decides to withdraw from the trial, the investigator must aim to undertake procedures similar to those for V32, FU1 and FU2 (see section 8.1.5) as soon as possible after the last dose of trial product.

The end-of-trial form must be completed, and final drug accountability must be performed even if the subject is not able to come to the trial site. A treatment discontinuation session must be made in the IWRS and the subject should be registered as withdrawn in the eCRF. The case book must be signed.

Although a subject is not obliged to give his/her reason(s) for withdrawing from a trial, the investigator must make a reasonable effort to ascertain the reason(s), while fully respecting the subject's rights. Where the reasons are obtained, the primary reason for not completing the trial must be specified on the end-of-trial form in the eCRF.

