Unless otherwise specified, all continuous measurements will be summarised descriptively at each visit by treatment using on-treatment observed data. Endpoints are summarised by arithmetic mean, standard deviation (SD), median, and minimum and maximum value. Selected endpoints, e.g. endpoints that are analysed log-transformed, will be reported with geometric mean and coefficient of variation in place of mean and SD. For measurements over time, mean values will be plotted to explore the trajectory over time. Observed data will be used as the basis for plotting data if not otherwise specified. For endpoints that are summarised with geometric mean, the geometric mean values will be plotted. Mean profiles for the primary and continuous confirmatory secondary endpoints by time of treatment discontinuation and treatment will be plotted in order to investigate discontinuation patterns. In addition, selected endpoints will be summarised by empirical distribution, box and mean change from baseline over time plots.

The primary objective is to confirm the effect of IDegLira in terms of glycaemic control in subjects with T2DM on previous treatment with SGLT2i ± OAD therapy. The primary estimand for the primary objective will be the difference in change from baseline in HbA_{1c} after 26 weeks between T2DM subjects randomised to IDegLira and IGlar, both in combination with SGLT2i ± OAD, regardless of whether subjects remained on initially assigned treatment or not until week 26. This estimand is a de facto estimand addressing effectiveness. With the aim of comparing treatment strategies this estimand is considered clinically relevant. It resembles the ITT principle. For the confirmatory secondary endpoints de facto estimands addressing effectiveness are chosen as primary estimand too.

The secondary estimand for the primary objective will be the difference in change from baseline in HbA_{1c} after 26 weeks between T2DM subjects randomised to IDegLira and IGlar, both in combination with SGLT2i ± OAD, attributable to randomised treatment, if all randomised subjects had tolerated and adhered to treatment until week 26. This estimand is a de jure estimand addressing efficacy. In the non-inferiority setting this estimand has higher assay sensitivity than an effectiveness estimand. The estimand is considered clinically relevant since it provides information to treating clinicians about the glycaemic efficacy attributable to IDegLira for the purpose of

CONFIDENTIAL

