(V32A) from subjects prematurely discontinued from randomised treatment. To estimate this estimand for evaluation of non-inferiority of HbA_{1c}, a pattern mixture model approach³⁵ will be adopted. It mimics an ITT scenario where withdrawn and prematurely discontinued subjects from the investigational treatment (IDegLira) arm not having a week 26 measurement are assumed to be switched to a treatment inferior to comparator (IGlar) or any other treatment received after premature treatment discontinuation. This corresponds to a jump to reference (J2R) principle where a penalty in terms of the NI margin is added to withdrawn or prematurely discontinued subjects in the IDegLira arm. Observe that the J2R principle and use of retrieved (V32A) data in analyses will equalise treatment effects and in turn assay sensitivity in the non-inferiority setting may be jeopardized. The penalty of the non-inferiority margin³⁶ is to remedy this. Multiple copies (1000 copies) of the full dataset will be generated by imputing missing values based on estimated parameters for a subgroup of subjects in the trial. This will be done as follows:

- As a first step, all post-randomisation HbA_{1c} values for prematurely discontinued subjects in the investigational treatment group (IDegLira) not having retrieved (V32A) data are set to missing
- In the second step, intermittent missing values are imputed using a Markov Chain Monte Carlo (MCMC) method, in order to obtain a monotone missing data pattern. This imputation is done for each treatment group separately and 1000 copies of the dataset will be generated. Subjects from either group with retrieved (V32A) data will now have a non-missing data pattern
- In the third step, for each of the 1000 copies of the dataset, an ANOVA model with pre-trial OAD and region as factors, and baseline HbA_{1c} as covariate is fitted to the change in HbA_{1c} from baseline to first planned HbA_{1c} measurement visit after randomisation (V10) based on the control group (IGlar) and subjects with retrieved (V32A) data in the investigational group (IDegLira). The estimated parameters, and their variances, from this model are used to impute missing values at the first planned HbA_{1c} measurement visit after randomisation (V10) for subjects in both treatment groups, based on their pre-trial OAD, region and HbA_{1c} at baseline

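### From subjects considering withdrawal, sites are told to secure the early end-of-treatment visit rather than the week-26 visit V32A that the primary analysis needs; sections 6.6, 8.1.7 and 8.1.8 should be reconciled

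*Protocol*

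**What the plan says.** Section 6.6 gives three instructions that bear on this point.

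- It defines withdrawal narrowly. "Only subjects who decline any further contact with the site in relation to the trial", and who therefore will not report end-of-trial endpoint information, count as withdrawn.
- For subjects still deciding, it says: "Subjects who consider withdrawing informed consent should be encouraged to have procedures performed according to the EoT visit and the two follow-up contacts", with a pointer to the flow chart.
- It closes with: "Please see section 8.1.7 for procedures to be performed in case of subject withdrawal".

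Section 8.1.7 covers subjects who stop trial product early, including at their own will. They have the EoT visit, FU1, FU2 and phone contacts every four weeks, and then: "The subject should finally come in for a V32A at week 26 to report MACE". At that visit HbA1c, body weight and total daily insulin dose are also obtained.

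Section 8.1.8 covers subjects who have decided to withdraw. For them "the investigator must aim to undertake procedures similar to those for V32, FU1 and FU2", soon after the last dose. V32A is not mentioned.

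Sections 17 and 17.3.1 define the primary estimand as the difference in HbA1c change after 26 weeks "regardless of whether subjects remained on initially assigned treatment or not until week 26". Step 1 of the primary analysis says that post-randomisation HbA1c values of prematurely discontinued IDegLira subjects "not having retrieved (V32A) data are set to missing".

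Amendment 2 makes V32A a fasting visit and renames the imputation methods. It leaves 6.6, 8.1.8 and step 1 unchanged.

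**The concern.** A treatment-policy estimand needs a week-26 measurement from subjects who have stopped trial product, and V32A is the visit that supplies it. The sentence telling sites what to ask of a wavering subject names three other contacts. Of these, only the EoT visit includes HbA1c. If an IDegLira subject attends it but never attends V32A, step 1 removes the result from the primary analysis.

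These are the subjects for whom the request matters most. Someone willing to attend an EoT visit and two further contacts has not yet declined all contact, so by the definition in 6.6 is not withdrawn and could be asked for week 26.

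What is at stake is how far the results depend on imputation. That covers the non-inferiority result and the superiority tests for body weight, HbA1c and insulin dose. Section 17.4.1.1 runs those three through the same model without the penalty step, so step 1 carries over to them. A week-26 value not collected at the time cannot be obtained later.

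**Working it through.** **1. The passages side by side**

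| Place | Applies to | Contacts named | V32A |
|---|---|---|---|
| 6.6, encouragement | considering withdrawal | EoT visit, two follow-ups | not named |
| 6.6, last sentence | withdrawal | refers to 8.1.7 | by reference only |
| 8.1.7 and flow chart footnote 1 | trial product stopped early | EoT, FU1, FU2, four-weekly phone contacts, V32A | yes |
| 8.1.8 | decided to withdraw | procedures as for V32, FU1, FU2 | no |
| 18.2 | withdrawn, separate consent | cardiovascular information at planned end of treatment | no HbA1c |

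Section 6.6 sends withdrawal to 8.1.7, but the section on withdrawal is 8.1.8, and its list is shorter. The two cannot both be the withdrawal procedure.

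**2. What happens to the HbA1c of an IDegLira subject who attends only the encouraged contacts**

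- The EoT visit yields an HbA1c. FU1 and FU2 do not (flow chart, 8.1.5).
- Step 1: without V32A, that value and all earlier post-randomisation values are set to missing. The baseline value is kept as a covariate.
- Steps 3 to 5: values from V10 to V32 are imputed from a model fitted to IGlar subjects and to IDegLira subjects with V32A data.
- Step 6: 0.3% is added to the week-26 value of every prematurely discontinued IDegLira subject, whether that value is retrieved or imputed.

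V32A therefore changes the value used, not the penalty. Step 1 does not apply to IGlar, so early IGlar values stay in.

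**3. Timing**

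Week 26 is day 182, and the ±3-day window opens on day 179. FU2 falls 30 to 33 days after the last dose. 179 − 33 = 146 days (20.9 weeks) and 179 − 30 = 149 days (21.3 weeks). For subjects stopping before about week 21, the encouraged contacts end before the week-26 window opens.

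**4. How many subjects could be affected**

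Section 6.1 expects 354 of 416 to complete on trial product. This agrees with the 15% used elsewhere: 0.85 × 416 = 353.6. Discontinuers: 416 − 354 = 62, or 0.15 × 208 = 31.2 per arm. The documents give neither a V32A retrieval rate nor a consent-withdrawal rate. If retrieval were 0%, 50% or 100% (assumption), about 31, 16 or 0 IDegLira subjects would have all post-baseline HbA1c set to missing.

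**5. Illustrative shift in the treatment difference D**

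Approximately, shift = (k₁δ₁ − k₂δ₂)/208. Here k is the number of recovered week-26 values in IDegLira (1) and IGlar (2), and δ is the measured minus the imputed value. All inputs below are assumptions.

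- Consent withdrawn by 25% to 50% of 62: 15.5 to 31 subjects.
- One third to one half of these would attend V32A: 5.2 to 15.5, hence 2.6 to 7.8 per arm.
- δ of 0.3% to 1.0% in IDegLira and zero in IGlar: 2.6 × 0.3/208 = 0.004% up to 7.75 × 1.0/208 = 0.037%.
- Equal δ in both arms: about zero.
- δ in IGlar only: −0.004% to −0.037%.

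The largest value is 0.037/0.3 = 12% of the margin and needs every assumption at its extreme with no offset. No sample-size or power figure is affected.

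**The case against.** The best defence is that the protocol already leads to V32A. The encouragement sentence points to the flow chart, whose first footnote includes V32A for anyone stopping trial product. The last sentence of 6.6 points to 8.1.7. Section 6.4 says that stopping treatment is not withdrawal, and 8.1.7 does not treat a missed phone contact as withdrawal. So a subject willing to attend at week 26 is already in follow-up. Section 8.1.8 deals with people who have made up their minds, so a list of early procedures is natural there. Dependence on imputation is also examined, through MMRM with retrieved data, the conditional analysis that omits step 1, and a tipping-point analysis.

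Much of this stands. A reader might infer that the protocol gives these subjects no route to V32A, or that 8.1.8 mishandles the undecided; the text supports neither. What remains is that the flow-chart pointer is attached to the EoT visit and follow-ups, that the cross-reference leads to a section on a different event, and that the withdrawal section omits V32A. A site reading the operative sentence would not learn that week 26 is what matters. Sensitivity analyses show how much the assumption matters but do not supply the missing value.

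The early EoT visit is not wasted. It serves safety, the conditional and MMRM analyses, and the IGlar side of the primary analysis.

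**Conclusion.** The point holds as a cheap improvement. For subjects considering withdrawal, the instruction to sites and the data needs of the primary, body weight and insulin-dose analyses do not match, and 6.6, 8.1.7 and 8.1.8 do not agree on the procedure. This rests on the text alone, with one reading: that step 1 treats a subject who withdraws consent as prematurely discontinued, as the description of the approach in 17.3.1 indicates.

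The size cannot be derived from the documents. Under the assumptions shown, it is a few hundredths of a percentage point of HbA1c at most, which is probably small against 0.3%. The direction is uncertain because values would be recovered in both arms and discontinuers move to other marketed treatment (5.4).

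Three stronger conclusions might be drawn, and none is supported:

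- **V32A spares an IDegLira subject the penalty.** Step 6 adds it either way.
- **Subjects without V32A are imputed purely as IGlar.** The model also uses IDegLira subjects with retrieved data.
- **The non-inferiority result is biased in a known direction.** Nothing in the documents establishes this.

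**What to change.** Reconcile 6.6, 8.1.7 and 8.1.8 so that one procedure applies, and correct the cross-reference at the end of 6.6. In 6.6 and 8.1.8 state an order of requests:

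1. A subject considering withdrawal is first asked to stay in the trial off trial product under the 8.1.7 follow-up.
2. Only if that is declined is the subject asked to attend V32A at week 26 alone, for HbA1c, fasting body weight and insulin dose.
3. Those who accept either are followed as prematurely discontinued and are not registered as withdrawn.

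Keep the encouragement to attend EoT, FU1 and FU2. V32A alone should be the fallback, not the first offer, so that four-weekly SAE and MACE collection is not given up needlessly.

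The cost is a few sentences and matching subject information. The downside is less frequent SAE and MACE information for the few who accept only V32A.
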